11.0 SAFETY ANALYSES

The safety analysis will be performed using the Safety Population. The safety parameters will include adverse events (AEs) and clinical laboratory, vital sign physical examinations, post-void residual (PVR) urine volume, catheterization usage (in particular clean intermittent catheterization (CIC) for urinary retention), and bladder and kidney ultrasound results. For each safety measurement the last nonmissing safety assessment before the first dose of study treatment will be used as the baseline for all analyses of that safety parameter. Continuous variables will be summarized by number of participants and mean, SD, median, Q1, Q3, minimum, and maximum values. Categorical variables will be summarized by number and percentage of participants.

11.1 ADVERSE EVENTS

Adverse events will be coded by system organ class and preferred term using the Medical Dictionary for Regulatory Activities (MedDRA).

An AE will be considered a treatment-emergent adverse event (TEAE) if it was present after the first dose of study treatment or was present before the date of the first dose of study treatment and increased in severity or became serious after the first dose of study treatment.

The number and percentage of participants reporting TEAEs in each treatment group will be tabulated by descending percentage in any treatment group, by system organ class and preferred term, and further categorized by severity and causal relationship to the study drug and instillation procedure. If for a given preferred term more than 1 AE is coded to the same participant, the participant will be counted only once for that preferred term using the greatest severity for the summarization by severity and causal relationship.

Separate participant listings will be generated for deaths, serious adverse events, and TEAEs leading to study discontinuation.

To assess possible distant spread of toxin (PDSOT), 39 MedDRA preferred terms that may be associated with botulinum toxin effects have been identified. All AEs associated with PDSOT will be listed by participant. The 39 terms are listed below.

MedDRA Preferred Terms Evaluated for Possible Distant Spread of Toxin

Cardiac Disorders

Bradycardia

Eye Disorders

Accommodation disorder
Diplopia
Extraocular muscles paresis
Eyelid function disorder
Eyelid ptosis
Pupillary reflex impaired
Vision blurred

Gastrointestinal Disorders

Constipation
Dry mouth
Dysphagia
Ileus paralytic

Infections and Infestations

Botulism

Musculoskeletal and Connective Tissue Disorders

Muscular weakness

Nervous System Disorders

Bulbar palsy
Cranial nerve palsies multiple
Cranial nerve paralysis
Dysarthria
Facial paralysis
Facial paresis
Hyporeflexia
Hypotonia
Paralysis
Paresis cranial nerve
Peripheral nerve palsy
Peripheral paralysis
Speech disorder
Vocal cord paralysis
Vocal cord paresis

Renal and Urinary Disorders

Urinary retention

Respiratory, Thoracic and Mediastinal Disorders

Aspiration
Diaphragmatic paralysis
Dysphonia
Dyspnoea
Pneumonia aspiration
Respiratory arrest
Respiratory depression
Respiratory failure

Reproductive System and Breast Disorders

Pelvic floor muscle weakness

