**7.1.2. Day of Treatment Criteria**

The following day of treatment criteria must be fulfilled prior to administration of study treatment at randomization/Day 1:

- Central laboratory urine analysis results for possible UTI have been reviewed

[figure not shown]
**BOTOX® (Botulinum Toxin Type A)  
Purified Neurotoxin Complex**

- Negative urine dipstick reagent strip test (for nitrates and leukocyte esterase) performed at the study site
- Participant is asymptomatic for a UTI, in the opinion of the investigator
- Negative urine pregnancy test for women of childbearing potential
- Investigator continues to deem that no condition or situation exists which, in the investigator's opinion, puts the participant at significant risk from receiving an intravesical instillation of BOTOX

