## **9. Study Assessments and Procedures**

- Study procedures and their timing are summarized in the schedule of activities ([Section 2](#)).
- Protocol waivers or exemptions are not allowed.
- Immediate safety concerns should be discussed with the sponsor immediately upon occurrence or awareness to determine if the participant should continue or discontinue study treatment.
- Adherence to the study design requirements, including those specified in the schedule of activities, is essential and required for study conduct.
- All screening evaluations must be completed and reviewed to confirm that potential participants meet all eligibility criteria. The investigator will maintain a screening log to record details of all participants screened and to confirm eligibility or record reasons for screening failure, as applicable.
- Screening procedures can commence once the informed consent and data authorization/protection form have been obtained. Screening will be considered to have started at the time of the first screening activity or procedure, and completed when all the required inclusion/exclusion criteria have been met and the patient is randomized at Day 1.

**BOTOX® (Botulinum Toxin Type A)  
Purified Neurotoxin Complex**

Screening procedures should be completed as soon as possible, with a maximum of -14 day window from randomization/Day 1 for Stage 1 and maximum of -28 day window from randomization/Day 1 for Stage 2. The patient will be considered enrolled into the study upon randomization at Day 1. If the patient has a positive urine dipstick test result and needs to be treated for a UTI, the screening period can be extended by up to 14 days. Screening procedures may be repeated during this time, as deemed clinically necessary, at the discretion of the investigator (eg, repeat the 3-day bladder diary if patient had a symptomatic UTI during initial diary collection).

- Evaluations should be performed by the same evaluator throughout the study whenever possible.

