### 9.2.1. Time Period and Frequency for Collecting AE and SAE Information

All SAEs from the signing of the ICF until 30 days after the last follow-up visit will be collected at the timepoints specified in the schedule of activities ([Section 2](#)), and as observed or reported spontaneously by study participants.

All AEs from the signing of the ICF until the last follow-up visit will be collected at the timepoints specified in the schedule of activities ([Section 2](#)), and as observed or reported spontaneously by study participants.

Medical occurrences that begin before the start of study treatment but after obtaining informed consent will be recorded on the AE section of the eCRF.

All SAEs will be recorded and reported to the sponsor or designee within 24 hours, as indicated in [Appendix 3](#). The investigator will submit any updated SAE data to the sponsor within 24 hours of it being available.

Investigators are not obligated to actively seek AE or SAE information in former study participants. However, if the investigator learns of any SAE, including a death, at any time after a participant has been discharged from the study, and he/she considers the event to be reasonably related to the study treatment or study participation, the investigator must promptly notify the sponsor.

The method of recording, evaluating, and assessing causality of AEs and SAEs and the procedures for completing and transmitting SAE reports are provided in [Appendix 3](#).

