#### **9.2.6. Study-Specific Definitions for Particular Adverse Events**

##### Definition of Adverse Event of Urinary Retention

An adverse event of urinary retention should only be recorded when a participant has an elevated PVR that requires intervention with CIC according to the following criteria:

- Participant has a PVR of  $\geq 350$  mL (regardless of symptoms), OR
- Participant has a PVR  $\geq 200$  mL and  $< 350$  mL and the participant reports associated symptoms ie, voiding difficulties, sensation of bladder fullness that in the investigator's opinion require CIC.

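### Both SAPs define a treatment-emergent AE by presence after dosing, so an unchanged screening AE qualifies as written; the effect is small and the fix is one sentence in each

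*SAP*

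**What the plan says.** The definition is the same in section 11.1 of both SAPs. Its first clause reads: "An AE will be considered a treatment-emergent adverse event (TEAE) if it was present after the first dose of study treatment". The second, joined by *or*, takes an AE that was there before the dosing date and "increased in severity or became serious after the first dose of study treatment". The join itself is explicit: an AE counts "if it was present after the first dose of study treatment or was present before the date of the first dose". The first clause requires neither a start date on or after dosing nor absence before it.

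The flag governs the counts and percentages of participants with TEAEs by system organ class and preferred term, the breakdowns by severity and causal relationship, and the listing of TEAEs leading to discontinuation. Section 4.0 of the Stage 2 SAP adds a pooled summary of AE data from the first 12 weeks of each stage, without saying whether it uses the same flag.

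Protocol 9.2.1 sets the collection period: "All AEs from the signing of the ICF until the last follow-up visit will be collected". It also states: "Medical occurrences that begin before the start of study treatment but after obtaining informed consent will be recorded on the AE section" of the eCRF. Protocol section 9 allows Stage 2 screening a "maximum of -28 day window from randomization/Day 1 for Stage 2". Stage 1 has 14 days, and a positive dipstick can extend either by up to 14 more.

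**The concern.** An AE that begins in screening and simply continues is, in plain terms, present after the first dose. It satisfies the first clause without any change. Nearly every AE that the worsening clause was written to catch is also present after dosing, so under this reading that clause is almost redundant. A definition that empties half of itself is unlikely to be what its authors meant, but it is what a programmer is told to implement.

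Comparing safety with placebo is a stated objective, and TEAE tables are the main display for it. Events that predate dosing cannot have been started by treatment. Counting them raises the rate in every arm and moves the ratio of BOTOX to placebo towards 1. Two programmers could also build different flags, each with some support in the text.

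**Working it through.** **1. The plan's own safety figures.** No stated figure depends on the TEAE definition. The nearest are the Stage 1 probabilities of at least one event among BOTOX-treated participants (Protocol 10.1; Stage 1 SAP 13.0), from 1 − (1 − p)^n:

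| n on BOTOX | retention, p = 6% to 7% | UTI, p = 20% to 30% |
|---|---|---|
| 8 | 0.390 to 0.440 | 0.832 to 0.942 |
| 16 | 0.628 to 0.687 | 0.972 to 0.997 |

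These agree with the plan.

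**2. The definition against the other AE rules in the same SAPs.**

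- 15.5 and 15.6 sort AEs by whether they started before, or on or after, the dosing date. Onset wording was available but is not used in 11.1.
- 15.5 assigns mild to a pre-dose AE with missing severity. Read literally, 11.1 would carry such an event into the TEAE severity table as mild.
- 15.6 fills in missing causality only for AEs that started on or after dosing. A carried-over AE with missing causality has no rule for the causality table.
- 15.7 imputes AE start dates only. If presence after dosing decides the flag, a screening AE turns on its stop date, for which there is no imputation rule.
- 11.2 excludes participants already abnormal at baseline from the laboratory PCS percentages. The first clause of the AE definition has no matching protection.

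**3. Size of the dilution.** Let p be the true rate of new or worsened AEs and b the proportion with an unchanged screening AE that runs past dosing. Assume b is equal across arms and independent of p.

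- Tabulated rate = 1 − (1 − p)(1 − b)
- Tabulated risk difference = (1 − b) × true risk difference

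The documents give neither b nor placebo rates, so both are assumptions. With true rates of 40% on BOTOX and 30% on placebo:

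| b | BOTOX | placebo | difference (points) | ratio |
|---|---|---|---|---|
| 0 | 40% | 30% | 10.0 | 1.33 |
| 5% | 1 − 0.60 × 0.95 = 43% | 1 − 0.70 × 0.95 = 33.5% | 9.5 | 1.28 |
| 10% | 1 − 0.60 × 0.90 = 46% | 1 − 0.70 × 0.90 = 37% | 9.0 | 1.24 |
| 20% | 1 − 0.60 × 0.80 = 52% | 1 − 0.70 × 0.80 = 44% | 8.0 | 1.18 |

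The ratio is more sensitive when rates are low. With 20% against 10%, b = 1% gives 9.9 points and a ratio of 1.91 instead of 2.00; b = 5% gives 9.5 points and 1.66. For a single preferred term, b is the carry-over for that term alone, so it cannot exceed the b for any TEAE.

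In the planned Stage 1 arms of 8 or 16 on BOTOX, one carried-over AE in a participant with no other TEAE moves the any-TEAE rate by 1/8 = 12.5 or 1/16 = 6.25 points. By chance it may fall in either arm.

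**4. Where carry-over can occur.** The day-of-treatment criteria (Protocol 7.1.2) require a negative dipstick and state: "Participant is asymptomatic for a UTI, in the opinion of the investigator". An AE of UTI itself requires symptoms (Protocol 9.2.6). For the other event of interest, Protocol 9.2.6 says: "An adverse event of urinary retention should only be recorded when a participant has an elevated PVR that requires intervention with CIC". The triggers for CIC in Protocol 9.4.4 and 9.4.5 are post-treatment PVR findings. For both terms b should therefore be close to zero. The dilution would fall on other terms and on the any-TEAE rate.

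**The case against.** The strongest reply is that the intent can be recovered from the text. Sections 15.5 to 15.7 work from AE start dates, and the worsening clause has a purpose only if the first clause means new onset. A programmer who reads the whole SAP would probably build an onset-or-worsened flag. This stands to the extent that miscounting is a risk of the wording and not a certain outcome. It does not remove the defect, because those sections do not restate or override the definition.

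The reply is also right about scale and reach. Findings at the screening physical examination go to the medical history page, not the AE page (11.4.1), which limits carry-over. Safety results are descriptive, with no safety test or risk ratio specified. The distant-spread listing covers all AEs, and the death and SAE listings are not restricted to TEAEs. The data review committee works from unblinded safety data, not expressly from TEAE tables.

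A reader might infer that the definition will hide a BOTOX safety signal. The documents do not support that. Over-counting raises the absolute BOTOX rate, the risk difference loses only the fraction b, and the two named events of interest are largely protected.

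**Conclusion.** The rule in 11.1 of both SAPs is wrong as written, with a small expected effect. Taken literally it admits AEs that began in screening and did not change, and it disagrees with the onset-based conventions in 15.5 to 15.7. The TEAE tables would be affected, as would the pooled 12-week summary if it uses the same flag.

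Under equal and independent carry-over, the risk difference shrinks by b as a proportion: from 10 points to between 9.5 and 8.0 for b of 5% to 20%. These values of b and the underlying rates are illustrations, not estimates. The case for correcting the text rests on an ambiguous flag that is cheap to repair, not on a large bias.

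**What to change.** Replace the definition in 11.1 of both SAPs with: *A TEAE is an AE whose start date is on or after the date of study treatment, or one present before that date that rose in severity or became serious on or after it.* State in section 4.0 of the Stage 2 SAP that the pooled 12-week AE summary uses this flag, if that is intended.

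Use the date and not the clock time, because 15.5 to 15.7 are date-based and the visible text does not show that AE onset times are collected. The cost is one sentence in each SAP. The small downside is that an event on Day 1 before instillation counts as emergent unless an onset time is recorded.

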**Table 10-3 Statistical Methodology**

Methodology	Description
Categorical counts	
 
Number of participants in individual categories           
 
Participants with <math>\geq 1</math> qualifying event counted once per individual category
 
 
 

Categorical descriptives	
 
Number and percentage of participants in individual categories           
 
Participants with <math>\geq 1</math> qualifying event counted once per individual category
 
 
 
N1 if percentage denominator <math>\neq</math> number of participants in the population (standard)
 

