#### 10.3.4. Safety Analyses

The following safety categories will be summarized as appropriate (eg, categorical or continuous descriptives, shift tables) for the safety population and will be fully defined in the SAPs.

[figure not shown]
- Adverse events

**BOTOX® (Botulinum Toxin Type A)  
Purified Neurotoxin Complex**

- Physical examination
- Vital signs (pulse rate, blood pressure, and body temperature)
- Urine dipstick reagent strip test
- Urinalysis (with urine culture/sensitivity, as applicable)
- Hematology and clinical chemistry
- PVR urine volume
- Kidney and bladder ultrasound
- Urine pregnancy test for women of childbearing potential
- Concomitant medications
- Concurrent procedures

Adverse events will be mapped to a Medical Dictionary for Regulatory Activities (MedDRA) preferred term and system organ classification (SOC) using MedDRA. For each adverse event reported, the number and percent of participants will be tabulated based on the preferred term. The tables will be generated by relationship to treatment as well as by system organ class and severity.

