15.5 MISSING SEVERITY ASSESSMENT FOR ADVERSE EVENTS

If severity is missing for an AE that started before the date of the dose of study treatment, an intensity of mild will be assigned. If severity is missing for an AE that started on or after the date of the dose of study treatment, an intensity of severe will be assigned. The imputed values for severity assessment will be used for the incidence summary; the values will be shown as missing in the data listings.

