15.6 MISSING CAUSAL RELATIONSHIP TO STUDY DRUG FOR ADVERSE EVENTS

If the causal relationship to the study treatment is missing for an AE that started on or after the date of the dose of study treatment, a causality of yes will be assigned. The imputed values for causal relationship to study treatment will be used for the incidence summary; the values will be shown as missing in the data listings.

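### Both SAPs choose among repeated adverse events by severity alone, so a treatment-related event can drop out of the causality table

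*SAP*

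**What the plan says.** Stage 2 SAP section 11.1 tabulates treatment-emergent events by system organ class and preferred term, "further categorized by severity and causal relationship to the study drug and instillation procedure". For repeated events of one preferred term it then sets a single rule: the participant is "counted only once for that preferred term using the greatest severity for the summarization by severity and causal relationship". Stage 1 SAP section 11.1 has the same sentence. Neither SAP states a strongest-relationship rule, and neither says which event to use when two have equal severity.

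Protocol section 10.3.4 also asks for a causality breakdown: "The tables will be generated by relationship to treatment as well as by system organ class and severity". The protocol's general convention for categorical summaries (Table 10-3) is that a participant has at least one "qualifying event counted once per individual category".

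Two imputation rules bear on the point. For a post-dose event with missing causality, "a causality of yes will be assigned" (section 15.6). For a post-dose event with missing severity, the SAPs assign severe (section 15.5).

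**The concern.** Taking the worst severity is the natural choice for a severity table. For a causality table the question is whether the participant had any event judged related, and the most severe event need not answer it.

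The design makes mixed judgements plausible. There is one catheter instillation on Day 1, followed by 12 weeks of follow-up in Stage 1 and 24 weeks in Stage 2. An early urinary tract infection may be judged related to the procedure and a later one not. UTI is one of the two adverse events of particular interest in Protocol section 10.1. Causality is recorded for both the study drug and the procedure, so one severity-selected record has to carry two separate judgements, and either can be lost. Stage 2 SAP section 4.0 also pools the first 12 weeks of adverse event data across stages, so the same rule could carry into the pooled tables.

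**Working it through.** No figure in the documents depends on this rule, so there is nothing to reproduce. The check is a reading of the text, a bound on the direction of the error, and an illustration of its size.

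**1. Worked case.** A participant has a mild UTI judged related and later a moderate UTI judged unrelated.

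| Rule | Severity table | Causality table |
|---|---|---|
| SAP 11.1 as written | moderate | not related |
| Protocol Table 10-3, once per category | mild and moderate, once each | related and not related, once each |
| Strongest relationship for causality | moderate | related |

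The last two rules both keep the participant in the related count. The SAP rule does not. An unrelated event with missing severity, set to severe under section 15.5, would displace a related mild or moderate event in the same way.

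**2. Direction.** The selected record is always one of the participant's own records. A participant shown as related therefore has at least one related event, while the reverse can fail. Selecting by severity can only match or undercount the number with any related event.

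**3. Size, for UTI.**

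From the documents:
- UTI rate u = 20% to 30% in the BOTOX-treated population of previous studies (Protocol 10.1).
- 53 participants per Stage 2 arm (Stage 2 SAP 13.0).

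Assumed, because the documents give no values:
- A share q = 10% to 30% of participants with a UTI have a second one, and none has more than two.
- Each event is related with probability r = 0.2, 0.5 or 0.8.
- There are three severity grades with shares s, and severity is independent of relatedness.

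For a participant with two events:
- P(related event displaced by a strictly more severe unrelated one) = 2r(1−r) × (1 − Σs²)/2
- P(at least one related event) = 1 − (1−r)²

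For mild/moderate/severe shares of 60/30/10, Σs² = 0.36 + 0.09 + 0.01 = 0.46, so (1 − 0.46)/2 = 0.27.
- r = 0.2: 0.32 × 0.27 = 0.086; at least one related = 0.36; share lost = 24%
- r = 0.5: 0.50 × 0.27 = 0.135; at least one related = 0.75; share lost = 18%
- r = 0.8: 0.32 × 0.27 = 0.086; at least one related = 0.96; share lost = 9%

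For other severity shares, the share lost at r = 0.2, 0.5 and 0.8 is:
- 80/18/2: 15%, 11%, 5%
- equal thirds: 30%, 22%, 11%

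Expected number displaced per BOTOX arm = 53 × u × q × P(displaced), with shares 60/30/10:
- lowest: 53 × 0.20 × 0.10 × 0.0864 = 0.09
- highest: 53 × 0.30 × 0.30 × 0.135 = 0.64

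This is about 0.1 to 0.6 participants, or 0.2 to 1.2 percentage points (0.09/53 and 0.64/53).

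**4. Ties.** With the same shares, P(mixed causality at equal severity) = 2r(1−r) × 0.46. That is 15% of two-event participants at r = 0.2 or 0.8, and 23% at r = 0.5. For these the SAPs give no rule at all.

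**The case against.** The strongest reply is that the sentence is loosely worded and could mean a two-step rule: restrict to related events first, then take the greatest severity among them. The protocol's once-per-category convention points the same way, and both SAPs place table specifications in a separate document that is not available here. The programmed table may therefore be right. This limits the point to what the SAPs say. It does not remove it, because the two-step rule is written in neither SAP and severity is the only selector named.

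Several further limits stand:
- The loss needs repeated events of one term in one participant, mixed causality, and a strictly more severe unrelated event.
- Protocol section 9.2.6 requires symptoms, a positive culture and leukocyturia for a UTI. Episodes that miss these criteria are recorded under other terms, which restricts repeats.
- The tables are descriptive, and the rule applies equally to every arm.
- Concealment is partial: "Separate participant listings will be generated for deaths, serious adverse events, and TEAEs leading to study discontinuation". Events on the possible distant spread of toxin list are also listed by participant. That list includes urinary retention, the other event of interest. It does not include UTI, and section 11.1 names no listing of all adverse events. A listing would not correct a tabulated rate in any case.

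A reader might infer a contradiction with section 15.6. There is none. Section 15.6 fills a missing value on one record and section 11.1 chooses among records, so both can be applied together. The selection rule is only the less conservative of the two.

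**Conclusion.** The point holds as a minor defect in a stated rule. As written, section 11.1 of both SAPs can place a participant with a related event in the unrelated row. This departs from the protocol's counting convention, and Stage 2 SAP section 16.0, which lists changes from the protocol, mentions only the ANCOVA factors. Total incidence and the severity table are unaffected.

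The likely size for UTI is about 0.1 to 0.6 participants per BOTOX arm of 53. Only the UTI rate and the arm size come from the documents. Recurrence, relatedness, severity shares and independence are assumptions. The 20% to 30% rate describes BOTOX-treated participants, so the range does not extend to placebo.

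Two stronger readings are tempting. The first is that related events are hidden as a matter of course. The documents show only that they can be, under the conditions above. The second is a larger loss: 0.30 × 0.35 × 0.25 = 2.6 points, or about 1.4 of 53 participants. That needs 35% recurrence and displacement in 25% of those participants, and the documents support neither. Under independence with three severity grades, displacement cannot exceed 0.5 × (2/3)/2 = 16.7%. A value of 25% would need unrelated repeats to be systematically more severe than related ones.

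**What to change.** In section 11.1 of both SAPs, split the rule. For several events of one preferred term, use the greatest severity for the summary by severity and the strongest relationship for the summary by causal relationship. Make the causality selection separately for study drug and for instillation procedure, because the event most related to one need not be the event most related to the other. This also settles ties in severity. Align the table specifications, including those for the pooled 12-week adverse event tables, with the revised text.

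The cost is one phrase in each SAP and a check of the programming. No new data are needed. The only downside is that related-event rates may come out slightly higher.
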